**Gain-framed messages and NRT for lung cancer screening patients ( Pro00055397 )**  
**PI: [name]**  
**Version 13 (11/14/2022)**

**SPECIFIC AIMS**

Screening for lung cancer at earlier, more treatable stages has the potential to reduce mortality from the US's most deadly cancer. The US Preventive Services Task Force (USPSTF) now recommends annual screening for lung cancer with low-dose computed tomography (LDCT) for high risk individuals based on age and smoking history. The Center for Medicare and Medicaid Services (CMS) recently approved annual lung cancer screening for its beneficiaries when conducted in centers offering comprehensive programs that include advice on smoking cessation. While it has been suggested that LC screening is a potential teachable moment, most current smokers seen for screening have variable motivation to quit, and many are unwilling to engage in a formal cessation program. Thus, there is a strong need to address smoking cessation across this continuum, catalyzing treatment engagement and cessation among all. The interventions in this study are broad and translational – effectively promoting quitting among all smokers and doing so in a way that is easily disseminable. In the context of 3 lung cancer screening programs (MUSC, VA and Yale) this project will evaluate a more intense yet still feasible intervention to enhance patient motivation to make and succeed in a quit attempt.

Our group has established effective tobacco interventions that demonstrate increased quit attempts and smoking cessation from: 1) gain-framed messaging, and 2) nicotine replacement therapy (NRT) sampling. Based on the tenets of Prospect Theory and an accumulating body of evidence from our previous studies, messages emphasizing the benefits of smoking cessation (i.e., gain-framed) are more effective than messages emphasizing the risks of continued smoking (i.e., loss-framed) for increasing intentions to quit, quit attempts, and smoking cessation in general populations of smokers. Our work also includes several studies showing that sampling of cessation medications leads smokers (both motivated and not) to increased cessation. Together, gain framed messaging and NRT sampling offer a novel and compelling opportunity to engage smokers and catalyze cessation. Our methods, if shown to be successful, can be easily shared with lung cancer screening programs across the country. Thus, we plan to conduct a randomized trial of gain-framed intervention (yes vs. no) x NRT sampling (2-week supply of both nicotine patch and lozenge vs. not) within a high-risk group of smokers (N=367) across 3 study sites (MUSC, VA and Yale). This study is powered to examine main effects of our 2 interventions:

**Primary Aim 1:** *To determine if the rate of smoking cessation among lung screening patients is improved by delivering gain-framed smoking cessation messages and delivery of a free starter package of medication (gain-framed behavioral intervention + 2 weeks of nicotine patches and lozenges vs. unframed behavioral intervention + no medication).*

**Hypothesis 1:** Cessation rates will be significantly higher at 6-months after lung screening for the smoking cessation strategy involving a gain-framed intervention + 2 weeks of nicotine patches and lozenges compared to a strategy of an unframed behavioral intervention + no medication. We define cessation as 7-day point prevalence but will assess multiple definitions of success.

**Exploratory Aim:** *To examine mediators and moderators of treatment to determine mechanisms of treatment effects and which subgroups are most likely to respond to the gain-framed and medication interventions, and to explore differential effects of the study factors across treatment groups. Treatment interactions will also be explored secondarily.*

[figure not shown]
**Hypothesis:** Changes in self-efficacy, smoking cessation outcome expectancies, familiarization with NRT, motivation, and autonomy will act as mechanisms for the smoking cessation effects (i.e., will act as mediators of treatment). Lung screening findings (e.g., presence of a nodule, cancer, etc), nicotine dependence, and health disparities will modify treatment response (i.e., will act as baseline moderators of treatment).

**Exploratory Aim:** *To examine additional treatment endpoints: patient reach, intervention fidelity, patient acceptance and engagement, cost, and the ease of delivery and feasibility.*

**Hypothesis:** We hypothesize that this project will be a low-cost feasible intervention that will reach a majority of patients who are smokers, with high adherence to and acceptance of the critical intervention elements.

Our rigorously designed study will be the first to demonstrate the individual and combined effects of gain-framed messaging and NRT sampling in a lung cancer screening population, which is a high-risk, difficult to

treat group of smokers in need of feasible, easily administered interventions, thus offering strong potential for clinical and population impact.

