
**Figure 1: Conceptual Model for Gain-Frame Messages and NRT**

*such test of this hypothesis, which, when presented in the context of a teachable moment, i.e., lung screening, offers additional clinical and public health significance.*

In the proposed study, we integrate these 2 complementary approaches to test a gain-framed intervention specifically designed for lung screening patients (vs. unframed messaging), as well as evaluating NRT sampling (vs. no medication). These interventions are complementary in that the evidence shows they will both lead to higher quit rates. Yet they are functionally somewhat independent. The evidence shows that self-efficacy may be a mediator for both. However, the other mediators are independent – outcome expectancies is specific to gain-framed messaging and familiarization with NRT, motivation, and autonomy are specific to NRT sampling. The primary hypothesis is that gain-framed messages designed specifically for lung screening patients will be especially persuasive when promoting smoking cessation (a prevention behavior), and thus can be utilized to further improve standard counseling for lung screening patients. Further, we hypothesize that sampling NRT in the lung screening population of smokers will also promote smoking cessation in addition to the standard counseling and gain-framed intervention. While our study is based on a 2x2 design, we are appropriately focused on the effect of combined treatment (vs. neither) and main effects (of either treatment); interactions are explored but cannot drive our scope as such a study would be wholly infeasible (>5,000 participants). Our project is designed to be translational (in that it can be transferable from our controlled efficacy study to other lung screening programs).

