### **Design and Methods:**

#### **General overview:**

We propose a group comparison study (gain-framed intervention vs. unframed intervention, starter package of 2 weeks of nicotine patches and lozenges vs. no medication) to evaluation methods to boost rates of smoking cessation for a high-risk group of smokers (N=367) with varying levels of motivation across 3 study sites (MUSC, Ralph H. Johnson Veteran Administration and Yale). All eligible study participants will be randomized to receive either: 1) Unframed Messaging (hereafter referred to as UM) with no medication, or 2) Gain-framed Messaging + Meds (i.e., 1 gain-framed video and print materials + 2 week starter pack of NRT; hereafter referred to as GM+M).

**Participants:** Our target sample will be 367 lung screening patients who currently smoke at each of 3 study sites: MUSC), Ralph Johnson VA, and Yale Cancer Center); Total N=367. The following eligibility criteria will ensure that we obtain our study sample of lung screening patients. **Inclusion:** 1) 50 years or older (we see no reason for an upper limit given supportive evidence for cessation among elderly), 2) at least a 20 pack year history of smoking (i.e., the base population of high risk smokers to get screened) as assessed by the patients ordering healthcare provider or the research team, 3) current smoker (defined as any smoking in the past 30 days – this is the criteria our lung cancer screening programs will use to trigger tobacco treatment interventions), 4) willing to be randomized, 5) English speaking; **Exclusion:** 1) unstable psychiatric/medical conditions such as suicidal ideation, acute psychosis, severe alcohol dependence, or dementia, and 2) known allergy to adhesives, and 3) current participation in another tobacco treatment program (e.g., using medication from a primary care doctor, quitline, etc).

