### **Statistical Considerations**

#### **Power and Sample size:**

We propose to test the primary hypothesis that rates of smoking cessation will be significantly higher 6-months after lung screening for the smoking cessation strategy involving a gain-framed intervention + 2 weeks of nicotine patches and lozenges compared to a strategy of an unframed behavioral intervention + no medication. We assume a biologically confirmed 7-day point prevalence abstinence rate at the 6 month follow up visit of 10-13% for the participants randomized to receive no NRT or gain framed messaging based on USPHS guidelines (Table 6.7 and 6.8 of USPHS Guidelines). In studies with a similar 2 week NRT exposure, 6 month abstinence rates varied from 16-34 % and a conservative estimate of a 20% abstinence rate in those receiving NRT only will be assumed. Based on previous work we estimate that the abstinence rate of in those receiving both NRT and gain framed messaging will be 10-11% increased over those with unframed messaging. Based on these estimates, we will have 80% power with a type 1 error rate of 5% to detect the conservative difference of between those receiving gain framed messaging + NRT (28%) and those receiving unframed messaging and no NRT (13%) with 123 participants randomized to each of the 4 treatment groups (total n=492 Participants). This assumes that the two treatment sites are moderately correlated (ICC=0.85) and randomize equal numbers of patients to each treatment cell. Additionally, we anticipate that 15-20% of our participants will fail to report 6 month follow up outcome data (LTF, death, moved out of area), accounting for a 20% attrition during the study follow up, we would need to randomize **n=367 participants** across all sites (179 randomized at Yale and 179 between MUSC and the VA) to maintain adequate power to detect the clinically meaningful difference stated. Assuming an abstinence rate of 14-17% in the group receiving unframed messages, we will have >80% power with a type 1 error rate of 5% to detect an 11% increase in abstinence in those receiving gain framed messages with the sample size stated for aim 1. We considered but opted against powering our trial on the treatment interaction, as this would require >5,000 participants.

Anticipated abstinence rates – 6 months	Gain-framed Intervention	No Message Intervention	
2 week starter pack NRT	28-30%	18-20%	23-25%

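### The Specific Aims claim power for the main effects of both interventions at N=367; no design in the documents delivers it

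*Combined protocol and SAP*

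**What the plan says.** The Specific Aims describe a "randomized trial of gain-framed intervention (yes vs. no) x NRT sampling". The sample is given there as 367 smokers at three sites, and the section then says "This study is powered to examine main effects of our 2 interventions". The Significance section, in the text after Figure 1, repeats the theme: "While our study is based on a 2x2 design, we are appropriately focused on the effect of combined treatment (vs. neither) and main effects".

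Under Design and Methods, the General overview describes a different allocation: "All eligible study participants will be randomized to receive either: 1) Unframed Messaging (hereafter referred to as UM) with no medication". The alternative is gain-framed messaging plus the NRT starter pack. No other arm is listed. Primary Aim 1 and Hypothesis 1 compare only these two strategies.

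Power and Sample size returns to four groups of 123 (492 in total). It gives power for two contrasts:

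- The package against neither, 28% vs 13%, at 80% power and a 5% type 1 error.
- Framing: more than 80% power for an 11-point increase over 14-17%.

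It gives no power figure for NRT. Its table of anticipated six-month abstinence shows margins of 23-25% with NRT and 15-18% without, and of 24-27% with gain framing and 14-17% without. The Statistical Analysis section plans models with a term for each randomized condition. The Human Subjects section gives an enrolment total of 616.

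**The concern.** A main-effects power claim covers two separate contrasts, yet the plan calculates only one of them. The uncalculated one, NRT, has the smaller anticipated difference in the plan's own table. The claim is also attached to 367, whereas the four-group calculation beside it produces 492 before attrition. Finally, the current randomization has two arms, and two arms cannot separate two factors.

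What is at stake is how any separate NRT or framing result would be read. If such an estimate were produced and came out non-significant, the sentence in the Specific Aims would make it look like adequately powered evidence of no effect.

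**Working it through.** **Inputs.** From Power and Sample size: type 1 error 5% (sidedness not stated), 80% power, 28% vs 13%, 123 per group, 20% attrition, and the table of anticipated rates. Sample sizes: 367 (Specific Aims), 492 (Power and Sample size), 616 (Human Subjects section). No site-clustering adjustment is applied, because the plan gives no formula for one.

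**Step 1: the plan's own figure.** For 28% vs 13% with a two-sided 5% test and 80% power, the two-proportion formula gives 113 per group without continuity correction and 126 with it. Power at 123 per group is 83.4% and 79.1% respectively. So 123 is reproduced closely by a two-sided test. Inflating for attrition, 492/0.8 = 615, which matches the 616 (4 x 154) in the Human Subjects section and not 367.

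**Step 2: two-arm allocation.** Every participant has either both factors or neither. The NRT indicator equals the framing indicator, so a model with both terms cannot separate them. No main effect is estimable and no power figure applies.

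**Step 3: differences implied by the table under a 2x2 layout.** Averaging cells:

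- NRT, low ends: (28+18)/2 = 23 vs (20+10)/2 = 15, a difference of 8 points.
- NRT, high ends: (30+20)/2 = 25 vs (23+13)/2 = 18, a difference of 7 points.
- Framing, low ends: (28+20)/2 = 24 vs (18+10)/2 = 14, a difference of 10 points.
- Framing, high ends: (30+23)/2 = 26.5 vs (20+13)/2 = 16.5, printed as 27 and 17, again 10 points.

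**Step 4: NRT power.** With n per level equal to half the total, d the difference and pbar the mean rate:

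Power = Phi( [d - 1.96 sqrt(2 pbar (1-pbar)/n)] / sqrt([p1(1-p1) + p2(1-p2)]/n) )

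For 23 vs 15 at n = 183.5: [0.08 - 1.96 x 0.04096] / 0.04074 = -0.007, so power is 49.7%. For 25 vs 18: [0.07 - 1.96 x 0.04289] / 0.04273 = -0.33, so power is 37.1%.

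| Total analysed | 23 vs 15 | 25 vs 18 | 25 vs 15 | 23 vs 18 |
|---|---|---|---|---|
| 367 | 49.7% | 37.1% | 66.9% | 21.9% |
| 492 | 61.9% | 47.2% | 79.4% | 27.8% |
| 616 | 71.7% | 56.2% | 87.5% | 33.6% |

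The first two columns pair like ends of the ranges. The last two are cross-pairings that no set of cells in the table implies.

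A two-factor logistic calculation on the four cells agrees: 49.9% and 37.4% at 367. Continuity correction lowers the like-end figures at 367 to 44.4% and 32.4%. With only the 80% who report outcomes (about 294), they are 41.5% and 30.8%. For 80% power, like-end pairing needs 754 (8 points) to 1,080 (7 points) analysed in total.

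**Step 5: framing power, same formula.**

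| Total analysed | 25 vs 14 | 28 vs 17 | 24 vs 14 | 27 vs 17 |
|---|---|---|---|---|
| 367 | 76.0% | 71.5% | 68.6% | 63.9% |
| 492 | 87.1% | 83.4% | 80.9% | 76.5% |
| 616 | 93.3% | 90.7% | 88.7% | 85.2% |

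The stated figure of more than 80% for 11 points therefore holds at 492 but not at 367.

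**Step 6: the primary comparison in two arms.** For 28% vs 13%, power is 94.8% with all 367 analysed (183.5 per arm) and 89.3% after 20% attrition (146.8 per arm).

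**The case against.** The strongest reply is that the trial is now a two-arm comparison of the package with neither, that Primary Aim 1 tests only this, and that the test is well powered. On that view the main-effects sentence is left over from a factorial plan and harms nothing. It is right that the primary test is sound, and right that 37-50% is not the trial's NRT power under two-arm allocation. A reader might infer that it is; the General overview does not support that, because in two arms the quantity does not exist. But the sentence is then less true, not more, and the factorial wording still stands in the current Specific Aims, Significance, Power and Statistical Analysis sections.

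A second reply is that the table gives ranges. A reader of the like-end results might infer that NRT could not be adequately powered at any size in the documents. That goes too far: 25% vs 15% gives 87.5% at 616. The same pairing gives only 66.9% at 367, the size to which the claim is attached.

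A third reply is that the test could be one-sided. At 367 that gives NRT 62% (23 vs 15) or just under 50% (25 vs 18), and 77.5% even for 25 vs 15. It would lift framing to 81-85% for 11 points, but only 75-79% for the table's 10. At the plan's stated 80% power, one-sided sizing gives 89 or 102 per group rather than 123; it gives 123 only at 90% power.

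Last, nothing in the plan says that a non-significant NRT result would be read as no effect. That misreading is a risk created by the sentence, not a stated intention.

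**Conclusion.** The sentence is wrong as written. At 367, the two-arm randomization makes both main effects inestimable. A 2x2 split would give about 50% or 37% power for NRT and 64% to 76% for framing. These figures assume a two-sided 5% test, equal groups, all 367 analysed, like ends of the table's ranges paired, and no site-clustering adjustment. The NRT shortfall at 367 survives every alternative pairing and sidedness examined. The framing shortfall depends on a two-sided test or on the table's 10 points.

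A reader might infer that only NRT is affected, because it is the effect with no calculation. The figures do not support that: framing also misses 80% at 367 under a two-sided test. Nor does the point weaken the package comparison, which keeps about 89% to 95% power. The documents do not say how 367 arose or label the 616 total as a superseded design, and the conclusion does not depend on either.

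**What to change.** In the Specific Aims, replace the sentence with wording such as:

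> The trial is powered for the comparison of gain-framed messaging + NRT with unframed messaging + no medication; it is not powered for the separate main effects of either intervention.

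Remove or qualify the main-effects focus in the Significance section and the framing power sentence in Power and Sample size. Reconcile the 2x2 language in the Specific Aims, Significance, Power and Statistical Analysis sections with the two-arm randomization in the General overview.

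If any factorial allocation does apply, label main-effect estimates exploratory, report them with 95% confidence intervals, and state that a non-significant result will not be read as no effect. Quote NRT power only as conditional on a 2x2 split. Putting 37-50% into the protocol without that condition would write a factorial figure into a two-arm plan.

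The cost is editing time and a less favourable stated claim. No enrolment is added and the primary comparison does not change.

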## RESEARCH STRATEGY

### A. Significance:

Cigarette smoking leads to more than 480,000 deaths annually in the United States. Smoking causes 30% of all cancer deaths and nearly 90% of all lung cancer deaths. While many of these deaths occur in former smokers, continued smoking remains an ongoing public health challenge, despite the remarkable progress that has been made in development of effective smoking cessation treatments. Lung cancer is now the leading cause of cancer death in both men and women in the US. In addition to primary prevention (tobacco control), secondary prevention through early detection is another strategy to reduce lung cancer death rates. More specifically, lung cancer screening with low-dose CT scans (LDCT) identifies lung cancer at an earlier, more treatable stage in high-risk patients. Evidence from the National Lung Screening Trial (NLST), for which MUSC was a study site, showed that screening with LDCT for high risk individuals (>30 pack years of smoking, <15 yr quit-time, and 55-74 yrs of age) conferred a 20% reduction in mortality for those patients who received 3 annual low dose CT scans. These findings led the USPSTF to recommend annual screening with LDCT for lung cancer in persons at high risk based on age and smoking history (grade B), with CMS and many private insurers now covering screening for this population. With an emphasis on the components necessary for a high-quality lung screening program^3 which includes smoking cessation efforts, comprehensive screening centers are opening across the nation. Tobacco treatment options offer limited success, thereby increasing the importance of smoking cessation for this population. Much is known about cessation within the general population, but less is known for lung screening patients. *The proposed study is the first study of a smoking cessation intervention specifically for patients enrolled in a clinical lung cancer screening program.*

While one might hypothesize that simply having a CT scan may promote cessation, evidence suggests that having a scan increases quit rates only slightly, if there is any increase at all. In a recent study, CT scanning prompted smoking cessation *shortly following the scan, especially when the results were abnormal.* However, long-term abstinence rates were similar for those with and without abnormal lung findings. Likewise, referral to a physician for an abnormal scan result may increase initial quit attempts but this is not always sustained. A recent evaluation of qualitative interviews from current smokers offered lung cancer screening showed that 49% of participants suggested that screening lowered their motivation for cessation. Misperceptions include the belief that negative screening offers protection from lung cancer; or the perception that screening can save lives by catching cancer early when indeterminate findings are identified that can be monitored; or a belief that a cancer-free screening test result indicates that they are among “the lucky ones” who will avoid the harms of smoking. There is of course no safe level of smoking, even among those who screen negative, and the need to effectively address cessation in the context of screening is profound. There is limited direction from the CMS memo regarding how to implement smoking cessation, with the option to provide very limited advice, which only has small effects. The present study is thus timely and novel – we will investigate whether we can achieve higher rates of short- and long-term cessation in a high risk population.

Gain-Framed Messages: Prospect Theory provides the foundation to assert the influence of health message framing for smoking cessation. Prospect Theory suggests that decision makers organize or “frame” information relevant to a health decision in terms of potential gains or potential losses, as compared to a present reference point (e.g., one’s current level of health). Factually equivalent material can be presented differentially to individuals such that they encode it as either a gain or a loss from this reference point. Prospect Theory summarizes these decision strategies by noting that individuals are, in general, *risk-seeking* in the domain of losses but *risk-averse* in the domain of gains. When behavioral choices involve risk, individuals will be more likely to take these risks when information is framed in terms of the relative disadvantages (losses or costs), and they will be more likely to avoid these risks when the information is framed in terms of the relative advantages (gains or benefits). The *type* of health behavior also influences the effects of message framing. Gain-framed messages are more effective in promoting physical exercise, sunscreen utilization, and smoking cessation, all prevention behaviors (e.g., McCall & Martin Ginis). In a secondary data analysis of the NLST, we demonstrated that former smokers in the control arm abstinent for 7 years had a 20% reduction in lung cancer specific mortality compared that of those screened with LDCT. Further, the combination of smoking abstinence and LDCT screening resulted in a 38% reduction in lung cancer mortality. This novel research will be an essential piece of the gain-framed messages specific to lung cancer risk reduction that we use in the proposed project. We emphasize, in line with Prospect Theory, that it is the *match* between a message frame (gain or loss) and the required health behavior (prevention or detection) that especially motivates behavior change. Gain-framed messages have been shown to be more effective than loss-framed messages for

[figure not shown]
increasing intentions to quit, quit attempts, and smoking cessation in general populations of smokers. Thus, the primary hypothesis for our message framing intervention is that *gain-framed messages are especially persuasive when promoting cancer prevention behaviors like smoking cessation, and thus can be utilized to further improve standard tobacco cessation counseling in the context of lung cancer screening.* We also believe that gain-framed messaging will have a particularly salient effect when presented in conjunction with a concrete, behaviorally-based cue to action as is offered through NRT sampling.

**Nicotine Replacement Therapy (NRT) Sampling** NRT sampling merely refers to providing short, starter packets of NRT, which can be easily added to existing counseling (message framing) protocols. Sampling is distinct from a full course of NRT treatment, in that the intent is to engage smokers in the process of quitting, but without any requirement or expectation to quit immediately and/or abruptly. It is a softer, gradual exposure to the quitting process that is conceptually designed to heighten smoker acceptance and enhance motivation and self-confidence. It is also rooted in marketing research (businesses have been doing this for years), which shows that brief exposure to a product, when provided for free, increases positive opinion and more importantly increases further use of that product.

There are several mechanisms by which gain-framed messages and NRT sampling, when offered in conjunction with lung cancer screening, could promote downstream changes in smoking behavior (quit attempts, abstinence; see **Figure 1**). We discuss these potential mediators for both interventions below. One is through improved self-efficacy. As smokers gain confidence in controlling smoking, they may be more likely to believe that total abstinence is possible. Changes in outcome expectancies have been shown to act as a mediator in our

previous gain-framed messaging research. NRT sampling might also heighten motivation. Whereas abrupt quitting is often daunting, gradual exposure to cessation, particularly when that experience is made easier through NRT, might remove some of the perceived barriers to quitting (e.g., “this isn’t so bad, I can do this”). A third mechanism is through increased familiarization with NRT. Many smokers continue to hold misperceptions about cessation pharmacotherapy, and particularly NRT. Misperceptions are broad, but typically pertain to concerns about 1) safety (e.g., addictive potential, adverse events), and 2) efficacy. In our prior efficacy trial of NRT sampling (discussed below), sampling of NRT yielded direct improvements in each of these mechanisms; i.e., increases in motivation, confidence, and knowledge/attitudes of NRT, which themselves are predictive of eventual cessation. Finally, while not an explicit outgrowth of self-determination theory, NRT sampling is wholly consistent with it; i.e., with the rationale that smokers will be more invested in the quitting process if they autonomously decide for themselves the goals and pace for changing tobacco use. Uptake of cessation treatment is higher when accessibility is increased, as would be the case when NRT is proactively provided at the point of lung screening. One older study examined outcomes of smokers in a cessation program who either received NRT for free, or paid for it. Use of NRT was higher when provided for free, as was long-term abstinence. Within tobacco control, the best example of NRT sampling is through quitlines. Evidence consistently shows that quitlines that offer free medication result in improved cessation rates as compared to quitlines that do not. Some but not all research suggests that 2-week provision of NRT is as cost-effective for promotion of quitting as is extended supply. However, whereas quitlines typically exclusively draw smokers who want to quit, we believe that NRT sampling is ideally suited to smokers across the motivational continuum, serving as a catalyst for treatment engagement among those who are not wanting to quit. *In the context of lung cancer screening, NRT sampling is particularly useful because it can be delivered on-the-spot (at the point of screening) and does not require specific training or skill. See below for prior and ongoing work within our group in support of NRT sampling. We believe that NRT sampling will have additional benefit when presented in concert with gain-framed messaging about quitting. This would be the first*
